Potential subjects will be patients of The Advanced Gynecologic Surgery Institute. They will be recruited pre-operatively in the office if they are scheduled to have a laparoscopic or robotic- assisted hysterectomy or myomectomy for symptomatic uterine fibroids at ALGH. The purpose, details, and consent for the study will be performed at that time. The study will then be re- discussed with the patients during the surgical consent process.

Patients currently sign a consent form for morcellation per Advocate Health Care guidelines

(Attachment A). They also sign a separate consent for morcellation in a bag specifically developed by The Advanced Gynecologic Surgery Institute (Attachment B). The alternative provided in this consent is to convert to laparotomy. The subjects will sign the existing consents as well as the research consent to participate in the study.

Study Timelines

- The duration of an individual subject’s participation in the study is only the time of their planned surgical hospitalization and their participation in the follow up pain assessments.
- The duration anticipated to enroll all study subjects is approximately one year.
- The estimated date for the investigators to complete this study is Fall 2016 / Spring 2017.

[figure not shown]
Study Endpoints

Primary endpoint: Leakage of egg albumin from the EcoSac bags after isolated bag morcellation or apparent leakage of specimen from the EcoSac bags during isolated bag morcellation.

Secondary endpoints:

- Intra-operative Complications (yes or no)
 - If yes to complications, please specify
- Post-operative Complications (yes or no)
 - If yes to complications, please specify
- Length of stay (hours)
- Admission (yes or no)
- Re-admission (yes or no)
 - If YES, yes to re-admission, specify reason_____
- Morcellation time (minutes) – from insertion of bag to removal of bag
- Technical issues with the use of the bag (yes or no)
- Conversion to open procedure (yes or no)
- Smooth muscle cell clusters in cytologic washings (yes or no)
- Post operative pain (Visual Analog Scale pain scale) (Figure 1)
 - Assessment times: immediate post-operative period (in the recovery room); 1 week post operatively; 2 weeks post operatively, and 4-6 weeks post operatively

Figure 1: Visual Analog Scale - Pain Scale

Other data to be collected include:

- Age
- Race
- Socioeconomic status (including educational level and annual household income)
- Weight
- Height
- Body Mass Index (BMI) (calculated)

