The integrity of the bag will be inspected. Once the bag is removed from the abdomen, it will be taken out of the operating room to the frozen section room. Five hundred milliliters of egg albumin (from egg whites) combined with 0.5 milliliters of methylene blue will be placed into the bag to assess for any leakage. The bag will be insufflated to a pressure of 25mmHg in a box trainer. A positive result will be documented if the egg albumin solution is present on the outside of the bag or dripping from any location. In current testing with Espiner Medical Ltd., egg albumin has been shown to not leak through the EcoSac 400 ECO-T (EMP 400 ECO-T) (Attachment C). The size of egg albumin is approximately 5.5 nm with a gram molecular weight (GMW) of 45,000. Although a hydrogen atom (0.1 nm, GMW 1), water (0.2 nm, GMW 18), and DNA (2 nm) are smaller than egg albumin, viruses and cancer cells are much larger (24-200 nm and 10,000-30,000 nm, respectively) (Attachment D).

Therefore, if egg albumin is unable to leak from the bag despite insufflation, fibroid cells or potentially cancerous cells will also be unable to leak from the bag.

The bag will then be disposed of in the normal post-operative manner in biohazard disposal bags.

Pain will be assessed per routine measures using the VAS pain scale in the post-anesthesia care unit. Patients will then receive a follow up phone call by a member of the research team to assess pain using the same VAS pain scale at 1 week post operatively and 2 weeks post operatively. The patient will have a final pain assessment at their post-operative office visit at AGSI 4-6 weeks post operatively.

The Espiner Medical Ltd. EcoSac 400 ECO-T (product number EMP400ECO-T) is an investigational device created to facilitate contained power morcellation. The bag is

made of Espiner Medical Ltd.'s unique Supramide66™ fabric, which is Polyurethane coated “ripstop” nylon fabric. According to Espiner Medical Ltd., the strong ripstop nylon material prevents the bag from bursting or rupturing. The bag will be removed in its entirety after morcellation and no device will be left in the abdomen. The morcellation will only be completed if adequate insufflation of the bag is obtained leading to appropriate visualization.

See attached for specifications of this device (Attachments E-K).

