ALGH = Advocate Lutheran General Hospital FDA = Food and Drug Administration

IRB = Institutional Review Board Ltd. = Limited

MIGS = Minimally Invasive Gynecologic Surgery N/A = Not Applicable

RNFA = Registered Nurse First Assistant SOP = Standard Operating Procedure

Description of devices

A detailed product description of the investigational devices proposed for use in this investigational plan can be found in their 510 (k) Premarket Notifications (Attachment K). Labeling for these devices will not be altered as this is an Investigator Sponsored IDE and we have no means of relabeling or over labeling the devices or providing revised instructions for use. How these devices will be used in this study is clearly detailed in the procedure section of the protocol (Investigational Plan)below.

Table 2: Morcellation Bag

ECOSAC 400ECO-T
White rip stop nylon bag Blue and green rip stop nylon tabs on mouth of bag Monofilament draw string Semi-automatic opening sac Radiopaque tab at bottom of bag

Multi port sleeve
Blue rip stop nylon
tab on sleeve
Four tabs on mouth
of bag: two blue, one
green and one orange
rip stop nylon tabs
Volume 4200Ml

Standard
laparoscopic trocars
used – 12mm trocar in
umbilicus and 5mm
trocars laterally
ECO-T sleeve
pulled through
lateral trocar
Laparoscope used
through lateral
trocar

ECOSAC 400ECO-T	
	Morcellator used in umbilical incision ECO-T sleeve tied off and pulled out of abdomen through umbilical incision
	Potential difficulty using sleeve due to trocar placement Better visualization of specimen and morcellator

Additional records and reports

Not applicable.

Methods, facilities, and controls

The EcoSac 400 ECO-T is not FDA cleared and will be available only to those participating in the study.

FDA has access to methods, facilities, and controls for both devices.

Amount charged for device

The device will be provided at no cost by Espiner Medical Ltd.

Device labeling

Labeling for these devices will not be altered as this is a Sponsor-Investigator IDE and we have no means of relabeling or over labeling the devices or providing revised instructions for use.

How these devices will be used in this study is clearly detailed in the procedure section of the protocol (Investigational Plan) below.

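### The bag test scores visible dyed liquid, so a negative result does not support the plan's inference, drawn from the 5.5 nm size of albumin, that cells cannot leak

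*Combined protocol and SAP*

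**What the plan says.** The first half of the primary endpoint (Study Endpoints) is "Leakage of egg albumin from the EcoSac bags after isolated bag morcellation". The second half is leakage of specimen that is apparent during morcellation.

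The bench test is described under Procedures Involved, EcoSac 400 ECO-T. The used bag receives "Five hundred milliliters of egg albumin (from egg whites) combined with 0.5 milliliters of methylene blue". Then: "The bag will be insufflated to a pressure of 25mmHg in a box trainer". The scoring rule is: "A positive result will be documented if the egg albumin solution is present on the outside of the bag or dripping from any location".

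The same section gives the reason for choosing albumin: "The size of egg albumin is approximately 5.5 nm with a gram molecular weight (GMW) of 45,000". It puts cancer cells at 10,000-30,000 nm and concludes that "if egg albumin is unable to leak from the bag despite insufflation, fibroid cells or potentially cancerous cells will also be unable to leak". The Objectives go further and treat the absence of leakage as confirming that the systems are safe and effective.

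**The concern.** The size comparison and the readout concern different things. The comparison is about which particles can pass through a pore. The readout is about whether enough bulk liquid has come through a hole, and stayed on the far side, for someone to see it. A negative reading therefore has a detection limit, and nothing ties that limit to 5.5 nm.

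At stake is what the primary result can be said to show. The inference errs in the unsafe direction: a bag with a perforation the size of a cell could be recorded as not leaking and then reported as proof against cells. The described procedures do not close the gap. The other half of the endpoint is also observational, and the cytologic washing is taken from inside the bag. The statistics section mentions abdominal and pelvic washings as an example variable, but the procedures describe no such collection.

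**Working it through.** The plan states no detection limit or sensitivity for the test, so there is no figure to reproduce. The check asks whether a cell-sized hole could be scored negative.

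**Inputs from the documents.** Pressure 25 mmHg; cell size 10-30 micrometres; albumin 5.5 nm; 500 mL of liquid (Procedures Involved); bag volume 4,200 mL (Table 2).

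**Assumptions.** Surface tension γ of 40-72 mN/m; contact angle θ at the hole exit from 10 to 90 degrees; liquid head of 0 or 10 cm; outer face in air. The last is inferred from the box trainer and the dripping criterion.

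**1. Size gap.** 10,000/5.5 = 1,818 and 30,000/5.5 = 5,455. The stated cells are about 1,800 to 5,500 times the size of the molecule on which the inference rests.

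**2. Largest hole that can hold liquid back.** 25 mmHg × 133.322 = 3,333 Pa. A 10 cm head adds 1,000 × 9.81 × 0.10 = 981 Pa, for a total of 4,314 Pa (32.4 mmHg). The limiting diameter is d = 4γ·sin θ/P. For example, 4 × 0.040 × 1/3,333 = 48.0 micrometres.

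| Exit contact angle | No head, γ = 40 to 72 mN/m | 10 cm head, γ = 40 to 72 mN/m |
|---|---|---|
| 90 degrees or more (not wetted) | 48.0 to 86.4 micrometres | 37.1 to 66.8 micrometres |
| 30 degrees | 24.0 to 43.2 | 18.5 to 33.4 |
| 10 degrees | 8.3 to 15.0 | 6.4 to 11.6 |
| Fully wetted | no such barrier | no such barrier |

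On a non-wetted face, the pressure needed to drive liquid out is 4γ/d: 120-216 mmHg for a 10 micrometre hole and 40-72 mmHg for a 30 micrometre hole, against 25 mmHg applied.

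**3. If the outer face is wet.** Visibility and time then set the limit. Poiseuille flow is Q = πPd⁴/(128μL), with assumed viscosity μ of 1-20 mPa·s and wall thickness L of 50-200 micrometres. A 10 micrometre hole passes about 0.01-1 microlitre/min, so an assumed visible 5 microlitres takes about 5 to 400 minutes, and no dwell time is stated. A 30 micrometre hole passes about 1-80 microlitres/min and would probably be seen.

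**4. Coverage.** 500/4,200 = 12% of the nominal volume. No rotation of the bag is described, so a hole above the liquid line would meet only gas.

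**5. Effect on the reported rate.** With 0 positives in 110 bags, the upper two-sided 95% limit is 1 − 0.025^(1/110) = 3.3% for test-positive bags. For truly breached bags it is 3.3%/s, where s is the test's sensitivity: 6.6% if s = 0.5 and 16.5% if s = 0.2. Both values of s are illustrative, because the text gives none.

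**The case against.** The strongest reply is that the surface-tension limits depend on a favourable surface state. The bag has just come out of the abdomen through the umbilical incision and no drying step is described, so a wet or partly wet outer face is at least as plausible as a dry one. At low contact angles the limit falls within or below the 10-30 micrometre range, and it vanishes on a fully wetted face. Contact with the trainer could also disturb a hanging meniscus. All of this stands. A reader might infer from the table that the test misses every hole below about 50-90 micrometres. The documents do not support that, since they give neither the wettability of the coated fabric nor the state of its outer face.

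Second, the endpoint itself is narrowly worded, and the disputed sentence is a rationale for the tracer, not a scoring rule. The failure named under Risks to Subjects is a tear, and the test should show large tears. This also stands, and it is why the test remains usable as a check of gross integrity. It does not rescue the sentence, which turns a visual negative into a statement about cells, or the Objectives, which build on no leakage.

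Third, Attachments C and D were not available and may contain a known-hole check or a detection limit. The text describes Attachment C only as showing that albumin did not leak, but a reader should not infer that the test was never validated. Nor do the documents show that cell-sized perforations occur in these bags.

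**Conclusion.** The inference from albumin size to cell containment is wrong as written. This conclusion needs no physical assumption. It rests on the scoring rule, which reads visible solution, and on the absence from the supplied text of any albumin assay outside the bag, dwell time or detection limit. A negative test supports no visible leak at 25 mmHg and nothing finer.

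The calculations show only that a cell-sized hole could be scored as no leak under plausible conditions. Across the assumed surface states the limit runs from 48-86 micrometres down to no surface-tension barrier at all, and even on a wet face a 10 micrometre hole could take too long to show. How often this would happen, if ever, cannot be determined from the documents.

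**What to change.** Under Procedures Involved, delete the sentence inferring that fibroid or cancerous cells cannot leak, and replace it with: *A negative test means no visible leak of dyed albumin solution at 25 mmHg; it does not establish containment at cellular size.* Carry the same limit into the primary conclusion and into the statement in the Objectives about confirming safety and efficacy.

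This is a text change. It needs no new data and no patient contact, and it leaves the scoring as it is. The price is a less absolute claim.

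The assay should not be altered now, for example by wetting the outer face. Prior Approvals lists monitoring-board reports and deviations, so the study appears to be under way, and a change would mix two sensitivities within one primary endpoint. A one-time bench check of the existing set-up on unused bags with holes of known size would give a detection limit to report. It is optional and not needed for the fix.

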Descriptive statistics (means and standard deviations or median and ranges) will be reported for all continuous variables (i.e. length of stay, age) based on their distribution and number and frequencies will be reported for all categorical variables (i.e. leiomyoma tissue or cells seen in abdominal and pelvic washings after isolated bag morcellation). Shapiro-Wilk's test of normality will be performed to assess the distribution of the continuous variables.

Efficacy analysis will be performed and will be included in the efficacy analysis. To confirm that the integrity of the bags is maintained throughout and after insufflation and power morcellation, safety analysis will be performed.

The intention to treat population will be used for the evaluation of the primary endpoint. All patients who receive the procedure will be included in the efficacy analysis.

Other exploratory / comparative analysis will be performed based on the number of patients with different characteristics. If comparative analyses are performed, Chi-square or Fisher's Exact test will be used for categorical variables and Student t-test or Mann-Whitney U test will be performed for the continuous variables. All analyses will be performed using SPSS for Windows, version 22.0 (SPSS Inc., Chicago, IL). A two-tailed p level of .05 will be considered statistically significant in all analyses.

Provisions to Monitor the Data to Ensure the Safety of Subjects

The James R. & Helen D. Russell Institute for Research & Innovation (Russell Research Institute) located at ALGH, will assign an independent monitor who will have the experience and medical training necessary to review patient medical files and conduct 100% source data verification of the case report forms used for study data collection. Monitoring will be done regularly, but at minimum after each 8 patients enrolled and treated in the study. Following is the monitoring plan:

- Provide onsite 100% Source Document Verification
- Monitor patient files on site in batches of 5-8 patients/ visit and at a minimum of monthly intervals during patient enrollment phase
- Provide written data discrepancy/omission report to principal investigator and IRB within 2 working days of the monitoring visit taking place
- Review patient data for protocol violations and expedite reporting according to FDA regulations and IRB approval requirement
- Review adverse events to ensure correct attribution of severity and causality and ensure timely reporting according to FDA regulations and IRB approval requirements

Conduct and reporting during the study will comply with the IDE regulations US 21 Code of Federal Regulations (CFR) 812, and Patient Protection regulations and IRB in 21 CFR 50 and 56, respectively. Of note, the Sponsor-Investigator has no financial interest in Espiner Medical Ltd. and may receive some financial assistance from Espiner Medical Ltd. or associated entities for the conduct of this study or subsequent publication and reporting of the data obtained during this study. Records will be kept in accordance with 21 CFR 54.

Withdrawal of Subjects

There is no anticipated voluntary withdrawal of subjects during the surgery. If, during the operation, it is decided that the specimen can be removed without morcellation, i.e. through the trocars or through the colpotomy, the patient will not be included in the study. Also, if the patient decides to withdraw from the study after the surgery, the patients' data that has been collected will be included in the analysis but no further data will be gathered. No patients will undergo morcellation unnecessarily for the purpose of the study.

Risks to Subjects

There is minimal increased risk to subjects beyond the standard surgical risks with introduction and removal of foreign body products during laparoscopy as well as the risk of morcellation as explained in the "Background" section of the protocol. The patients would have the same risk whether or not they were participating in the study as all of the subjects are planned and consented surgical patients. No patients will undergo morcellation unnecessarily for the purpose of the study. The use of the bags will not increase the risk to the patients. See 'Procedures Involved' and 'Withdrawal of Subjects' for further information.

There is a small potential risk of the bag tearing during morcellation leading to use of a foreign body without benefit of tissue containment. Were this to happen, a new bag would immediately be used and the abdomen and pelvis copiously irrigated. There is also a potential for decreased visualization of surrounding organs while the bag is insufflated. However, there should not be a risk of trauma to these surrounding structures because we will only be operating inside the bag and will be able to visualize everything inside the bag.

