Investigational plan

Protocol Title: Safety and efficacy of a contained electromechanical power morcellation systems for laparoscopic hysterectomy and myomectomy.

NCT#: NCT02777203

Date: 4/11/2017

Protocol Number: Pending. The study sponsor will be the Advanced Gynecologic Surgery Institute. The investigational site will be ALGH. The study will be reviewed by the Advocate Health Care Institutional Review Board (IRB) per appropriate protocol.

Objectives

The purpose of this feasibility study is to determine the safety and efficacy of using an insufflated bag for electromechanical power morcellation during laparoscopic hysterectomy and myomectomy for tissue removal. Our goal is to prove that the integrity of the bags is maintained throughout and after insufflation and power morcellation.

The hypothesis is that the bag will remain integral and there is will be no leakage from the bag during and after power morcellation using the described contained system, confirming the safety and efficacy of the systems.

Inclusion and Exclusion Criteria

Inclusion criteria will be adult premenopausal women (equal or greater than 18 years old) at ALGH without symptoms of menopause undergoing robotic or laparoscopic total or supracervical hysterectomies or myomectomies for the indication of symptomatic uterine fibroids who are not candidates for specimen removal via mini-laparotomy incision (as deemed by the study surgeon) or who have refused mini-laparotomy and therefore require power morcellation for tissue removal.

Exclusion criteria include known or suspected malignancy, peri- or post-menopausal women diagnosed with uterine fibroids, specimen that can be removed without power morcellation (e.g., vaginally or through laparoscopic trocars), and adults unable to consent.

These patients will be screened and consented pre-operatively. The final decision on a patient's inclusion or exclusion from the study will occur intra-operatively after evaluation of the size and characteristics of the uterus.

Study-Wide Number of Subjects

As this will be a feasibility study, a maximum of 110 patients will be enrolled into the study. Over a one year time, the investigation group performs a total of 130 hysterectomies and myomectomies; therefore, we anticipate 110 patients will be enrolled in this study during a three year timeframe.

Study-Wide Recruitment Methods

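### The plan treats an absence of leaks as proof of bag integrity, yet specifies only counts for the primary endpoint and no confidence interval; scoring of a torn and replaced bag is a smaller gap

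*Combined protocol and SAP*

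**What the plan says.** The Objectives section describes a feasibility study but sets a confirmatory aim: "Our goal is to prove that the integrity of the bags is maintained throughout and after insufflation and power morcellation". The hypothesis is that "there is will be no leakage from the bag during and after power morcellation using the described contained system", and this is taken as "confirming the safety and efficacy of the systems".

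On size, Study-Wide Number of Subjects says that "a maximum of 110 patients will be enrolled into the study". The figure is set beside a surgical volume of 130 procedures a year, with no power, margin or precision target.

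Study Endpoints defines the primary endpoint in two parts: "Leakage of egg albumin from the EcoSac bags after isolated bag morcellation or apparent leakage of specimen from the EcoSac bags during isolated bag morcellation". It also lists technical issues with the bag as a separate yes/no secondary endpoint.

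RESULTS/STATISTICS says that "number and frequencies will be reported for all categorical variables". It adds that a safety analysis will confirm bag integrity, but does not say what that analysis is. The named tests (Chi-square, Fisher, t, Mann-Whitney) apply only to optional comparisons between patients, and the two-tailed .05 level is attached to no test of the leak rate.

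On bags, Procedures Involved says "The integrity of the bag will be inspected" and describes the albumin test of the bag after removal, in the singular. Risks to Subjects foresees that a bag may tear during morcellation and be replaced by a new one during the operation.

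**The concern.** A count of zero out of a modest number of patients is an estimate with an upper limit. It does not show that the rate is zero. If the trial reports no leaks as a bare number and frequency and then draws the conclusion announced in its Objectives, readers will be told that integrity is proved when a leak rate of a few per cent has not been excluded. The endpoint concerns containment of tissue, and Procedures Involved itself raises the possibility of cancerous cells, so the rate that remains possible is what a reader most needs.

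Because the hypothesis is zero leaks, a single patient decides whether it is met. The scoring of a patient who needed two bags therefore matters, and the text does not say which bags are tested or how two bags give one patient result.

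**Working it through.** **No planned figure to reproduce.** The 110 has no statistical inputs. The check is what zero leaks in 110 would support.

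**Inputs.** n = 110 (Study-Wide Number of Subjects, a maximum); expected leaks = 0 (Objectives); two-sided 95% confidence, matching the two-tailed .05 level in RESULTS/STATISTICS. The true leak rates, the smaller sample sizes and the counts of failed bags below are illustrative assumptions, because the documents give none.

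**Upper limit with zero events.** The exact (Clopper-Pearson) two-sided 95% upper limit is 1 − 0.025^(1/n); the one-sided 95% limit is 1 − 0.05^(1/n).

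- n = 110: 1 − 0.025^(1/110) = 3.30% (one-sided 2.69%)
- n = 80 (assumed): 4.51%
- n = 50 (assumed): 7.11%

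**Chance of seeing no leaks when the bag does leak.** P(0 leaks in 110) = (1 − p)^110.

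- p = 0.5%: 0.995^110 = 57.6%
- p = 1%: 0.99^110 = 33.1%
- p = 2%: 0.98^110 = 10.8%

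**For scale.** The number of leak-free patients needed for a two-sided upper limit of p is ln(0.025)/ln(1 − p), rounded up: 183 for 2% and 368 for 1%.

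**Replaced bag.** Suppose that a first bag tears with no spillage seen, the replacement is intact, and no other patient has a leak. The primary result then depends on the scoring rule:

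- replacement bag only: 0/110, interval 0% to 3.30%
- any bag counts against the patient: 1/110 = 0.91% (0.02% to 4.96%)
- per bag: 1/111 = 0.90% (0.02% to 4.92%)

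With three such patients (assumed), the contrast is 0/110 against 3/110 = 2.73% (0.57% to 7.76%). These counts show only that the rule matters; they do not predict how often bags tear.

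**The case against.** The strongest reply is that this is a feasibility study, that the Objectives state a goal and a hypothesis rather than a decision rule, and that anyone given the count and the denominator can work out the interval. Part of this stands. A reader might infer that the plan has a formal criterion under which zero leaks is a pass. It has none. Nor do the documents show that 110 is too few: they state no acceptable leak rate against which to judge it. The one leak threshold, in Data Management, is an interim stopping limit printed as more than 110% of cases. No proportion can exceed that, so it supplies no benchmark; it needs separate correction. But feasibility status explains a modest sample and does not license a claim of proof, and leaving the interval to the reader does not correct the plan's own stated conclusion.

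On replaced bags, a reader might infer that any patient whose first bag tears would be scored as having no leak. The documents do not support that. The second part of the primary endpoint, apparent leakage of specimen during morcellation, would capture a tear with visible spillage, and nothing in Procedures Involved exempts a first bag from the albumin test. Risks to Subjects also calls the risk of tearing small. What remains is narrower: a tear without visible spillage, recorded only under "Technical issues with the use of the bag (yes or no"), with the patient scored on an intact replacement. The case report forms are not part of the text reviewed and could contain a rule.

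A reader might also press the loose wording of the analysis population. That is immaterial here: leaving out an assumed 3 patients moves the zero-leak upper limit only from 3.3% to 3.4%.

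**Conclusion.** The main point holds. As written, the plan would support its headline conclusion with a count alone, and that conclusion would not follow: zero leaks in 110 leaves true rates up to 3.3% open at the two-sided 95% level, and more if enrolment ends below the maximum. This needs no assumption beyond independent patients and a common leak rate. The 33% chance of zero leaks depends on an illustrative true rate of 1%.

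The replaced-bag point holds only as an ambiguity, limited to tears without seen spillage and to bags that damage makes untestable. Its size cannot be stated, since the documents give no tear rate. Confidence is high that the text reviewed specifies no interval and lower that no bag-level rule exists anywhere. The point should be fixed before analysis, but the data remain usable.

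**What to change.** In RESULTS/STATISTICS, specify that the primary leak rate is reported per patient with an exact (Clopper-Pearson) two-sided 95% confidence interval. Replace the language of proof and confirmation there and in the Objectives with the estimate and its upper limit, for example: no leaks in 110 patients; two-sided 95% upper limit 3.3%. Since no acceptable rate is stated, word this as an estimate and not as a pass.

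For patients with more than one bag, apply the albumin test to every study bag used. Score the patient positive in the primary analysis if any of her bags leaks, tears during morcellation, or cannot be tested because of damage. Add a sensitivity analysis restricted to the two leak components now in Study Endpoints, so that the result on the present definition stays visible. None of this touches how a torn bag is handled during surgery.

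The cost is one interval calculation, some rewording, and a bench test on any additional bags. The stated conclusion becomes less favourable, and scoring on any bag may raise the reported rate slightly. No extra patients are needed.
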